6.2 Infusion Duration Guideline

The decrease in the infusion duration for participants in cohorts 1 to 3 (with ≥30 kg body weight) will follow the flow presented in Figure 2. The decrease in the infusion duration for participants in cohort 4 (with <30 kg body weight) will follow the flow presented in Figure 3.

Please note that a participant is considered to tolerate the infusion duration when the infusion is completed within a duration not exceeding 120% of planned duration and no IAR is observed during the infusion.

[figure not shown]

Figure 2 Guideline for Decreasing Infusion Duration for Participants ≥30 kg

Abbreviations: IAR = infusion associated reaction.

Note: IARs occurring during a single infusion are counted as one IAR. Only when an IAR occurs in relation to a separate infusion will it be considered as a second IAR.

Note: When a second IAR occurs, the participant will discontinue study intervention and the previous highest rate tolerated by the participant will be considered as the maximum tolerated rate for this participant.

[figure not shown]

Figure 3 Guideline for Decreasing Infusion Duration for Participants <30 kg

Abbreviations: IAR = infusion associated reaction.

Note: IARs occurring during a single infusion are counted as one IAR. Only when an IAR occurs in relation to a separate infusion will it be considered as a second IAR.

Note: When a second IAR occurs, the participant will discontinue study intervention and the previous highest rate tolerated by the participant will be considered as the maximum tolerated rate for this participant.

6.3 Preparation, Handling, Storage, and Accountability

The Investigator or designee must confirm appropriate temperature conditions have been maintained during transit for all study intervention received, and any discrepancies are reported and resolved before use of the study intervention.

Guidance about reconstitution and dose preparation for Fabrazyme are provided in Appendix 2 (Section 10.2).

Only participants enrolled in the study may receive study intervention, and only authorized study site staff may supply or administer study intervention. All study intervention must be stored in a secure, environmentally controlled, and monitored (manual or automated) area in accordance with the labeled storage conditions with access limited to the Investigator and authorized study site staff.

The Investigator, institution, or the head of the medical institution (where applicable) is responsible for study intervention accountability, reconciliation, and record maintenance (ie, receipt, reconciliation, and final disposition records).

The Investigator, a member of the study site staff, or a hospital pharmacist must maintain an adequate record of the receipt and distribution of all study intervention using the Drug Accountability Form. These forms must be available for inspection at any time.

Further guidance and information for the final disposition of unused study interventions are provided in the Pharmacy Manual.

6.4 Measures to Minimize Bias: Randomization and Blinding

This is a single arm and open label study. No randomization or blinding will be implemented. The study intervention kits dispensing will not be managed within Interactive Response Technology. To minimize bias, the participant number will be assigned sequentially in the electronic case report form (eCRF) as the participants are enrolled into the study.

6.5 Study Intervention Compliance

The prescribed dosage, timing, and mode of administration may not be changed. Any departures from the intended regimen must be recorded in the eCRF.

Participants exhibiting poor compliance as assessed by visit attendance for their infusions should be counseled on the importance of good compliance to the study dosing regimen.

Non-compliance is defined as taking less than 80% of study intervention during any evaluation period (visit to visit).

Participants will be dosed at the study site and receive study intervention directly from the Investigator or designee, under medical supervision. The date and time of each dose administered in the clinic will be recorded in the source documents. The dose of study intervention and study participant identification will be confirmed at the time of dosing by a member of the study site staff other than the person administering the study intervention.

A record of the quantity of study intervention administered to each participant must be maintained and reconciled with study intervention and compliance records. The date, time of

start and stop of each infusion, as well as the dose and total volume infused, will also be recorded.

6.6 Dose Modification

Dose modifications are not planned or allowed in this study. Any dose deviation must be recorded in the eCRF.

6.7 Continued Access to Study Intervention After the End of the Study

The Sponsor will not be responsible for study intervention provision after the end of the treatment phase and after the end of the study. Continuing treatment after the end of the Study Intervention Period will be at the discretion of Investigator or treating physician.

The Sponsor will not provide any additional care to participants after they leave the study because such care should not differ from what is normally expected for participants with FD.

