	Treatment : Fabrazyme 1 mg/kg Q2W up to the rate tolerated (refer to Section 6.2), with oral premedications given 30 minutes prior to each infusion.
	Endpoint : Binary, calculated separately for each infusion duration: Participant achieved infusion duration without experiencing any IAR.
	Intercurrent events: A while-on-treatment approach will be applied. Participants never observed to tolerate any infusion rate will be counted as not achieving the required duration for the infusion. A treatment policy approach will be applied in case pre-medications are not given as described within the protocol. No action will be taken for this event for the analysis even when pre-medications are not given as described within the protocol.
	Summary measure : For each infusion duration, number and % of participants achieving the endpoint.

Objectives	Estimand Description/Endpoints	
	Population : Participants with confirmed diagnosis of FD, age 2 to 65 years, Fabrazyme-experienced, treated for at least 3 months without IARs during the most recent 3 infusions.	
	Treatment : Fabrazyme 1 mg/kg Q2W up to the rate tolerated (refer to Section 6.2), with oral premedications given 30 minutes prior to each infusion.	
	Endpoint : Binary, calculated separately for each infusion duration: Participant achieved infusion duration without experiencing a second IAR.	
	Intercurrent events: A while-on-treatment approach will be applied. Participants never observed to tolerate any infusion rate will be counted as not achieving the required duration for the infusion. A treatment policy approach will be applied in case pre-medications are not given as described within the protocol. No action will be taken for this event for the analysis even when pre-medications are not given as described within the protocol.	
	Summary measure: For each infusion duration, number and % of participants achieving the endpoint.	
Exploratory		
To investigate the influence of increased infusion rate on the immunogenicity and efficacy of	Changes of plasma lyso-GL3 from baseline to 6 months follow-up	
Fabrazyme treatment	Change of the titer of ADA to Fabrazyme over 6 months follow-up	
Safety		
To investigate the influence of increased infusion rate on the safety of Fabrazyme treatment	Number, severity, and nature of AEs including IARs	

Abbreviations: ADA = anti-drug antibody, AE = adverse event; FD = Fabry disease; IAR = infusion associated reaction; lyso-GL3 = globotriaosylsphingosine; Q2W = every 2 weeks.

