4.0 STUDY DESIGN

4.1 Overall Design

This is a Phase 4, prospective, open label, single arm, interventional study, to be conducted in the US, to evaluate the safety and tolerability of Fabrazyme at approved dose of 1 mg/kg with increases in the infusion rate and reduced infusion volume.

Up to 14 participants with FD will be enrolled to receive study intervention in 4 cohorts:

- Cohort 1: 3 Fabrazyme experienced female participants (body weight \geq 30 kg).
- Cohort 2: 3 Fabrazyme experienced non-classic male participants (body weight ≥30 kg).
- Cohort 3: 4 Fabrazyme experienced classic male participants (body weight ≥30 kg).
- Cohort 4: 4 Fabrazyme experienced participants (body weight <30 kg).

Classic FD is defined by α GAL level in dried blood spot or leukocyte below 3% of normal value and all others are considered as non-classic disease.

The study schema is presented in Section 1.2. Screening will be performed up to 4 weeks prior to the first dose of study intervention. All 4 cohorts of this study will be enrolled simultaneously. Enrolled participants will receive treatment for up to 16 weeks (up to 9 infusions) and have an End-of-Study Visit 28 weeks after the start of the treatment. Participants will undergo visits and study procedures as shown in Schedule of Activities (SoA) presented in Section 1.3.

All participants will receive Fabrazyme infusions at dose of 1 mg/kg at the study site. The participants are not required to stay at the site after completion of the infusion, unless the Investigator considers it medically necessary. The infusion duration will shorten, and the infusion rate will rise with each successfully tolerated infusion (ie, an infusion completed within a duration not exceeding 120% of planned duration, without infusion associated reaction [IAR]), until reaches the minimum infusion duration of 20 minutes for participants in cohorts 1 to 3 (≥30 kg) and 30 minutes for participants in cohort 4 (<30 kg). Guidance for increasing the rate of infusion (and consequently decreasing the infusion duration) are presented in Section 6.2. When the participant successfully reaches the shortest infusion duration planned for the cohort which he/she belongs, he/she will be considered a treatment completer and will not receive any further infusion as part of the study, regardless of whether the treatment period reaches 16 weeks or not.

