4.5 End of Treatment Definition

The end of treatment is defined when the participant successfully reaches the shortest infusion duration planned for the cohort which he/she belongs to or when the participant experiences a second IAR. At that point, the participant will not receive any further infusion as part of the study, regardless of whether the Study Intervention Period reaches 16 weeks or not (Figure 2 and Figure 3).

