9.3.4 Exploratory Endpoints Analysis

Table 7 Exploratory Endpoint Analysis

Endpoint	Statistical Analysis Methods
Changes of plasma lyso-GL3 from baseline to 6 months follow-up	The exploratory endpoints will be analyzed using descriptive statistics (cohort 1 to 4).
Changes of the titer of ADA to Fabrazyme from baseline to 6 months follow-up	

Abbreviations: ADA = anti-drug antibody; lyso-GL3 = globotriaosylsphingosine.

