4.5 End of Treatment Definition	The below paragraphs were edited (deleted text in strikethrough, additions in bold): The end of treatment is defined when the participant successfully reaches the shortest infusion duration planned for the cohort which he/she belongs to or when the participant experiences a second IAR. At that point, the participant will not receive any further infusion as part of the study, regardless of whether the Study Intervention Period reaches 16 weeks or not. The Study Intervention Period will be completed in the absence of IAR at Week 10, or at the latest at Week 16 (Figure 2 and Figure 3).	Correction on end of treatment definition, as in the absence of any IAR during the treatment period, if the current infusion duration for the participant ≥30 kg is 120 minutes (the shortest possible initial duration), then he/she would complete the treatment at Week 8; if the current infusion duration for the participant <30 kg is 90 minutes (the shortest possible initial duration), then he/she would complete the treatment at Week 6.

Section # and Name	Description of Change	Brief Rationale

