7.2 Intercurrent Events (ICE)

The intercurrent events in this study are defined as follows:

- ICE1 = Premature discontinuation of study treatment.
- ICE2 = Pre-medications are not given as described within the protocol.

The handling of the intercurrent events will be as follows:

For primary and secondary endpoints:

Management of ICE1 = A while-on-treatment approach will be applied in case of premature discontinuation of the study treatment, where the value of the endpoint will be derived from the infusions actually received.

Management of ICE2 = A treatment policy approach will be applied in the case pre-medications are not given as described within the protocol, meaning the value for the endpoint of interest will be used regardless of whether different pre-medications are given to those listed within the

Document: \\ieedc

Author:

vnasc01\BIOSdata\Sanofi\Fabrazyme\IAB16602\Biostatistics\Documentation\SAP\SAP\Sanofi\Final

Version\lps17726-16-1-9-sap.docx

Version Number: Final V1.0

Version Date: 22Oct2024

Template No.: CS_TP_BS016 Revision 7 Reference: CS_WI_BS005

Effective Date: 01Nov2021

PROTOCOL LPS17726

Analysis Plan Template

Page 32 of 65

protocol, administration of the pre-medications are different to what is provided on the protocol or in an absence of pre-medication being administered.

For exploratory endpoints:

Management of ICE1 = A treatment policy approach will be applied in the case of premature discontinuation of the study treatment, meaning the value for the endpoint of interest will be used regardless of whether study treatment was discontinued prematurely or not.

Management of ICE2 = A treatment policy approach will be applied in the case pre-medications are not given as described within the protocol, meaning the value for the endpoint of interest will be used regardless of whether different pre-medications are given to those listed within the protocol, administration of the pre-medications are different to what is provided on the protocol or in an absence of pre-medication being administered.

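### The Week 28 change in lyso-GL3 and ADA follows 12 to 22 weeks of physician-chosen treatment whose infusion duration need not be recorded, so by itself it cannot be attributed to the increased infusion rate

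*Protocol*

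**What the plan says.** **Objective and endpoint.** Protocol 3.0 states the exploratory objective: "To investigate the influence of increased infusion rate on the immunogenicity and efficacy of" Fabrazyme treatment. Protocol 9.3.4 names the endpoint as "Changes of plasma lyso-GL3 from baseline to 6 months follow-up", with a matching one for ADA titer. The Schedule of Activities (Protocol 1.3) places Month 6 at Week 28.

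**Length of study treatment.** Protocol 4.1 gives "treatment for up to 16 weeks (up to 9 infusions) and have an End-of-Study Visit 28 weeks after the start of the treatment". A participant who reaches the shortest planned duration "will not receive any further infusion as part of the study, regardless of whether the treatment period reaches 16 weeks or not". A second IAR also ends treatment (Protocol 4.5).

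**After study treatment.** Protocol 6.7 says the sponsor supplies no further drug, and "Continuing treatment after the end of the Study Intervention Period will be at the discretion of Investigator or treating physician".

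**What is recorded.** Protocol 6.5 requires start and stop times, dose and volume for each study infusion. For other medication, Protocol 6.9 asks for reason, dates, dose and frequency. The listing in SAP 13.3 adds route but no infusion duration.

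**Sampling.** Samples are taken before the study infusion. After early end of treatment, the only later visits kept for everyone are Week 12 and Week 28 (Protocol 1.3, footnote c).

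**Analysis.** SAP 3.3 extends the endpoint to every post-baseline visit. SAP 15.3.1.1.1 and 15.3.1.2.5 use all post-treatment samples. SAP 15.3.1.2.2 counts boosted and induced ADA at any time after first dosing, follow-up included. For premature discontinuation, SAP 7.2 applies a treatment policy, "meaning the value for the endpoint of interest will be used regardless of whether study treatment was discontinued prematurely or not".

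**The concern.** The objective is about infusion rate, but the named time point comes well after the study has stopped controlling, or requiring a record of, that rate. A stable Week 28 lyso-GL3 could be read as showing that faster infusion does no harm. A titer rise first seen in follow-up could be charged to faster infusion. Neither reading is safe unless one knows how the drug was infused in the intervening weeks.

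Two features of the analysis add to this. Week 12 can hold some participants still on study infusions and others who finished at Week 6 or 8. The boosted and induced ADA categories, and the incidence built from them (SAP 15.3.1.2.4), do not separate events arising on study infusions from events arising later.

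**Working it through.** **Inputs**
- At most 9 study infusions in 16 weeks, with End-of-Study at Week 28 (Protocol 4.1).
- Earliest finish with no IAR. For a participant of at least 30 kg starting from 120 minutes, "then he/she would complete the treatment at Week 8". For one under 30 kg starting from 90 minutes, Week 6. Both come from the rationale column of Protocol 10.6.
- Assumption: dosing every 2 weeks continues after study treatment, and the Week 28 sample precedes any infusion that day. The documents do not require either.

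**Check of the plan's own figure.** Study infusions = (last study week / 2) + 1. For Week 16: 16/2 + 1 = 9, as stated.

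**Formulas.** Let L be the week of the last study infusion.
- Weeks off study before the Week 28 sample = 28 − L.
- Two-weekly slots before that sample, Weeks 0 to 26 = 26/2 + 1 = 14.
- Off-study slots = 14 − (L/2 + 1).

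| L | Study infusions | Weeks off (share of 28) | Off-study slots of 14 | Next scheduled sample | Off-study slots before it |
|---|---|---|---|---|---|
| 6 | 4 | 22 (79%) | 10 (71%) | Week 12 | 2 |
| 8 | 5 | 20 (71%) | 9 (64%) | Week 12 | 1 |
| 10 | 6 | 18 (64%) | 8 (57%) | Week 12 | 0 |
| 12 | 7 | 16 (57%) | 7 (50%) | Week 28 | 7 |
| 14 | 8 | 14 (50%) | 6 (43%) | Week 28 | 6 |
| 16 | 9 | 12 (43%) | 5 (36%) | Week 28 | 5 |

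The range of 12 to 22 weeks covers participants treated at least to Week 6. Someone who stops sooner, for example at a second IAR at Week 2, has 28 − 2 = 26 weeks off.

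**Which columns mix on and off treatment.** Visits other than 1, 2, 3, 8 and 11 take place only while treatment continues. Scheduled Weeks 4 to 10, 14 and 16 are therefore on-treatment columns by design. Week 2 mixes only if someone stops after the first infusion. Week 12 mixes as soon as anyone finishes earlier. At Week 28 everyone is off study treatment.

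**What the on-treatment samples miss.** Each sample precedes that visit's infusion, and a completer's shortest infusion is the last one. No sample taken on study treatment therefore reflects the shortest duration.

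**ADA persistence.** SAP 15.3.1.2.3.1 needs positive samples at least 16 weeks apart. Scheduled post-baseline samples on treatment run from Week 2 to Week 16, a span of 16 − 2 = 14 weeks. On the planned schedule, a persistent response can be shown only with the Week 28 sample.

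**The case against.** A reader might infer that the 6-month endpoint mostly reflects routine, slower infusions at unrecorded rates, and that the study therefore cannot show any influence of rate. The documents do not support that reading, for five reasons.

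- **Mostly.** By infusion count, the off-study share exceeds half only when the last study infusion is at Week 10 or earlier. It is 36% at Week 16. The Week 6 and Week 8 timings assume the shortest starting duration and no IAR. The step charts (Protocol Figures 2 and 3) could not be read, so the usual finishing week is not known.
- **Slower.** Protocol 6.7 leaves continuation to the physician. Participants might keep the shortened duration, so the direction of any dilution is unknown.
- **Unrecorded.** This is true of duration only.
- **Cannot show.** The SAP summarizes every on-treatment visit and provides individual plots and per-cohort listings. It also defines each participant's end-of-treatment visit (SAP 6.4). With at most 14 participants, each series can be read against that date.
- **General mixing across visits.** It arises essentially at Week 12.

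The SAP 7.2 rule should also not be cited against completers. It covers premature discontinuation, and those who reach the target are treatment completers under SAP 6.4. What does hold is that neither SAP 7.2 nor any other section has a rule for off-study Fabrazyme after completion.

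Finally, this is an uncontrolled, descriptive, exploratory endpoint with no hypothesis, so causal attribution would be limited in any case. That argues for low severity. It does not remove the gap at Week 28, the pooling at Week 12 or the undivided ADA categories.

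**Conclusion.** The point holds for the Week 28 value and for the ADA categories, not for the whole by-visit table. Anyone treated to between Week 6 and Week 16 reaches the Week 28 sample after 22 to 12 weeks of treatment outside the study, which is 79% to 43% of the 28 weeks. If two-weekly dosing continues, 10 to 5 of the 14 preceding infusions are off study. The week counts need no dosing assumption; the infusion counts do.

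Because the duration of those infusions is not required to be recorded, the Week 28 change cannot by itself be attributed to the increased rate. The on-treatment summaries carry information on shortened durations but not on the last infusion, which for completers is the shortest. Severity is low: the change is worth making, but no primary or secondary result depends on it.

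**What to change.** 1. In SAP 15.3.1, add a summary of change from baseline at each participant's last pre-infusion sample on study treatment. State that it does not reflect the final infusion.
2. Label Week 28 as follow-up under physician-chosen treatment, and flag each participant's on- or off-study treatment status at Week 12.
3. Report treatment-boosted and treatment-induced ADA in two groups: first detected up to the first sample after the last study infusion, or later. Show the number of weeks since that infusion.
4. Record start and stop times of non-study Fabrazyme infusions to Week 28, and list them beside the Week 12 and Week 28 values.

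The first sample after the last study infusion should not become a main time point for lyso-GL3 or ADA titer. For anyone finishing at Weeks 12 to 16 it is the Week 28 sample itself, so the summary would pool Week 12 and Week 28 values. In item 3 the weeks since the last infusion are shown for that reason.

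**Cost.** A short addition to the SAP and a few eCRF fields. The on-treatment time point will differ between participants. The shortest duration will still not be captured unless a sample is added soon after the last study infusion (about 2 weeks), which would be a protocol change.

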6.8 Treatment of Overdose

Any dose of study intervention greater than the planned and approved dose will be considered an overdose.

Sponsor does not recommend specific treatment for an overdose.

In the event of an overdose, the Investigator should:

- Contact the medical monitor immediately.
- Evaluate the participant to determine, in consultation with the medical monitor, whether study intervention should be interrupted or whether the dose should be reduced.
- Closely monitor the participant for any AE/SAE and laboratory abnormalities until study intervention can no longer be detected systemically (depending on study intervention half-life).
- Document the quantity of the excess dose as well as the duration of the overdose.

